# 7.3 Clinical Laboratory Assessments

Laboratory assessments will be evaluated over time on study using descriptive statistics as described in Section 4.0. Clinical laboratory data will be summarized by study visit, cohort, and treatment group. Where appropriate, change from baseline in safety data will also be summarized in a similar manner.

## 73.1 Hematology

The hematology panel will include hemoglobin, hematocrit, red blood cell (RBC) count, platelet count, white blood cell (WBC) count, total neutrophils, eosinophils, monocytes, basophils, and lymphocytes.

## 7.3.2 Chemistry

Chemistry testing will include blood urea nitrogen (BUN), serum creatinine, total calcium, sodium, potassium, chloride, bicarbonate, magnesium, phosphate, uric acid, alanine transaminase (ALT), aspartate transaminase (AST), lactate dehydrogenase (LDH), alkaline phosphatase, total bilirubin (direct and indirect bilirubin reflexively measured only when total bilirubin is greater than the upper limit normal [ULN]), creatine phosphokinase, albumin, and total protein.

## 733 Fasting Serum Lipid Panel

The fasting serum lipid panel will include total cholesterol, high density lipoprotein cholesterol (HDL-C), calculated low density lipoprotein cholesterol (LDL-C) (Friedwald), triglycerides, very low density lipoprotein (VLDL). Non-HDL-C will be calculated as total cholesterol (TC) –HDL-C. When triglycerides are >400 mg/dL, another sample will need to be collected from the subject and a directly measured LDL will be done.

## 73.4 Urinalysis

Urinalysis testing will include pH, protein, blood, ketones, leukocyte esterase, and nitrites.

Microscopy is done if the dipstick sample is positive for blood, nitrites, leukocytes, and/or protein. A bacterial culture and sensitivity will be done if nitrites or leukocyte esterase are positive.

#### 735 Other Laboratory Tests

Other laboratory tests include serum follicular stimulating hormone (FSH) (women at screening to determine childbearing status), hemoglobin A1C (HbA1C), ultrasensitive C-peptide, urine pregnancy tests (screening and when necessary), screening serology for hepatitis B (HB) core and surface antigen/antibody (sAg/Ab), hepatitis C virus (HCV), human immunodeficiency virus (HIV) (1&2), Quantiferon, renal function evaluation via MDRD estimated glomerular filtration rate (eGFR) calculation, and thyroid stimulating hormone (TSH) (screening).

#### 73.6 Immunosuppression Troughs

A listing of immunosuppression troughs will be provided.

#### 7.3.7 Immune Panel

A listing of immune panel tests will be provided. The panel of immune function tests include:

- Humoral alloreactivity measured via human leukocyte antigen panel reactive antibody (HLA-PRA)
- Humoral autoimmunity measured via T1DM autoantibody titers of glutamate decarboxylase antibodies (GADA), insulin antibodies (IAA), islet antigen-2 antibodies (IA2A), and zinc transporter 8 (ZnT8)
- Cellular alloreactivity measured via mixed lymphocyte reaction (MLR)
- Cellular autoimmunity measured via lymphocyte stimulation test (LST)
- Cellular autoimmunity measured via Diab-Q Kit
- HLA typing of each subject (required to interpret the cellular immunity test results)

#### 7.4 Vital Signs

Vital sign data (weight, systolic and diastolic blood pressure, heart rate, and temperature) will be summarized by presenting descriptive statistics of raw data and change from baseline values at each study visit. A listing will also be provided.

#### 7.5 Physical Examination

A listing will be provided that includes the response to whether there are any clinically significant abnormal findings. This listing will be sorted by cohort, treatment group, and subject number.

#### 7.6 Other Safety Analyses

#### 7.6.1 Off-Target Growth

The number and percentage of subjects enrolled in VC02-101 Cohort 1 with off-target growth as evidenced by implanted VC-02 units via lumen ultrasound measurements, or by histological examination of explants will be summarized by cohort and treatment group.

#### 7.6.2 Immune Sensitization

The number and percentage of subjects enrolled in VC02-101 Cohort 1 with confirmed immune sensitization defined by presence of donor anti-HLA antibodies absent prior to implant in conjunction with either confirmatory histological observations from at least one explanted unit and/or the presence of clinical symptoms will be summarized by cohort and treatment group.

#### 7.6.3 Implant Tolerability

The number and percentage of subjects enrolled in VC02-101 Cohort 1 experiencing implant tolerability assessments (e.g., fever, erythema, pain, tenderness, induration) for up to four hours post-implantation and at subsequent visits, will be summarized by cohort and treatment group. Implant tolerability assessments include AEs that are Possibly Related or Definitely Related to investigational product or to the surgical procedure.

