#### 2.2.1. Primary Endpoint Measures

Primary Endpoint / Cohort 1:

- Targeted safety and tolerability profile, inclusive of:
  - The incidence of AEs with causality related to VC-02 combination product, the surgical procedures required for VC-02 administration, and the immunosuppressive drug regimen.
  - The incidence of off-target growth as evidenced by implanted VC-02 units via lumen ultrasound measurements, or by histological examination of explants.
  - The incidence of immune sensitization defined by presence of donor anti-HLA antibodies absent prior to implant.

- Implant tolerability assessments (e.g., fever, erythema, pain, tenderness, induration) for up to four hours post-implantation and at subsequent visits.

Primary Endpoint / Cohort 2:

• Change from baseline to Week 26 in C-peptide AUC0-4h following an MMTT.

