### 10.4.5.2. Secondary Safety Analyses

Unless otherwise specified, the SAS (both Cohort 1 and Cohort 2 subjects who meet the SAS criteria) will be used to summarize secondary safety endpoints. For the secondary safety endpoint of immune response as measured by serum immunoglobulin and hematological assays, any subject who appears to be having an immune response will have all relevant data described in a clinical narrative. In addition, data of interest from the assays may be summarized by treatment group and overall.

Changes in physical examinations will be summarized by treatment group and overall. Non-diabetic concomitant medications will also be summarized by treatment group and overall. Finally, implantation site assessments will be summarized at each time-point post-implantation and each visit thereafter. For each site assessment symptom, the number of subjects with the symptom at that time-point will be summarized by treatment group and overall.

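### SAP 7.6.3 omits the protocol's by-symptom, by-time-point tolerability summary and describes this Cohort 1 primary component through related AEs that are already tabulated elsewhere

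*SAP*

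**What the plan says.** **Endpoint.** Protocol 2.2.1 lists this as one part of the Cohort 1 primary endpoint: "Implant tolerability assessments (e.g., fever, erythema, pain, tenderness, induration) for up to four hours post-implantation and at subsequent visits". A different part of the same endpoint is: "The incidence of AEs with causality related to VC-02 combination product, the surgical procedures required for VC-02 administration, and the immunosuppressive drug regimen". Tolerability is also a secondary safety endpoint in section 2.2.2 of both documents.

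**Protocol analysis.** Under the secondary safety analyses (10.4.5.2), "implantation site assessments will be summarized at each time-point post-implantation and each visit thereafter". The next sentence gives the unit of count: "For each site assessment symptom, the number of subjects with the symptom at that time-point will be summarized by treatment group and overall".

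**SAP analysis.** SAP 7.6.3 plans "The number and percentage of subjects enrolled in VC02-101 Cohort 1 experiencing implant tolerability assessments", gives the same example symptoms, and continues "for up to four hours post-implantation and at subsequent visits, will be summarized by cohort and treatment group". It then adds: "Implant tolerability assessments include AEs that are Possibly Related or Definitely Related to investigational product or to the surgical procedure".

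**Rule for departures.** Protocol section 10 allows the SAP to modify the planned analyses, but major changes to endpoints or their analyses must appear in a protocol amendment. The SAP Revisions table records for 7.6.3 only that the section moved from 7.6.4.

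**The concern.** The two documents lead to different tables for the same endpoint. A programmer following the protocol would produce one row per symptom and one block per visit. A programmer following the SAP would have no stated breakdown by symptom or visit, and would have a content rule based on attributed cause instead of on what was observed at the implant.

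This is a first-in-human implant, and one exploratory objective is to optimise the surgical procedure, the anatomical site and perioperative care. That objective needs to know which local reactions occurred and at which visits. A percentage of subjects with product- or procedure-related AEs does not summarise that, and it adds little to the related-AE component beside it. The point concerns the content of the summary, not which cohort is tabulated.

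**Working it through.** There is no planned figure to reproduce, so the check sets the texts side by side and then counts the overlap.

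**1. What each text specifies.**

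| | Protocol 10.4.5.2 | SAP 7.6.3 |
|---|---|---|
| Unit | subjects | subjects |
| By symptom | yes | not stated |
| By time-point | yes, each one and each later visit | period named, no breakdown by it |
| Grouping | treatment group and overall | cohort and treatment group |
| Rule on cause | none | AEs possibly or definitely related to product or procedure |

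Both count subjects. The differences are the missing breakdown and the added cause rule.

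**2. Size of the missing table.** The protocol gives five example symptoms. The schedule has Day 1 (Visit 3) and then Visits 4 to 18, which is 15 visits. That gives 5 × (1 + 15) = 80 counts per treatment group. The symptom list is only illustrative, so 80 is indicative.

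**3. Whether another SAP section supplies it.** SAP 7.4 summarises vital signs by visit, which covers temperature only. SAP 7.5 is a listing of physical examination findings. The AE tables in 7.2.7 are by system organ class, preferred term, grade and relationship, never by visit. None replaces the symptom table.

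**4. How far the SAP rule reaches.** It has no stated limit to symptom or site. SAP 7.2.3 counts both implantation and explantation as the surgical procedure, so an explant-wound AE would meet the rule. A severe hypoglycemic event possibly related to VC-02 would also meet it if reported as an AE. A fever attributed only to immunosuppression would not, although fever is among the named symptoms.

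**5. Overlap with the related-AE summaries.** Each AE has three attributions: product, procedure and immunosuppression.

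- With three levels each (not/unlikely, possibly, definitely) there are 3³ = 27 patterns. The tolerability rule excludes those where product and procedure are both not/unlikely: 27 − 1×1×3 = 24. Any attribution at least possible: 27 − 1 = 26. The 2 patterns left over are AEs attributed only to immunosuppression.
- SAP 7.2.3 puts unlikely related into its combined related category. With four levels there are 4³ = 64 patterns. Tolerability rule: 64 − 2×2×4 = 48. Related to at least one factor: 64 − 1 = 63. Related to product or procedure (tables vii and viii of 7.2.7 together): 64 − 1×1×4 = 60.

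In each case the tolerability AEs lie wholly inside the related set. Tables vii and viii are restricted to treatment-emergent AEs, so for them the statement holds for treatment-emergent events. These are counts of patterns, not expected frequencies.

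**6. Whether the change is flagged.** The revision log marks other departures, such as the new definition of confirmed immune sensitization, as due for a later protocol amendment. For 7.6.3 it records no change of analysis, and the current protocol still carries the symptom-by-time-point text.

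**The case against.** The strongest counter-case is that little information is lost. SAP 7.2.7 tabulates product- and procedure-related events by preferred term. Its AE listing gives verbatim term, onset and resolution dates with study days, and outcome. Cohort 1 has at most 15 subjects, so a reader could trace reported reactions by hand. The protocol text in question sits under the secondary analyses and speaks of implantation-site assessments, and no symptom table is specified under the primary safety analysis (10.4.3). The protocol itself captures the first four hours through AEs (6.3, 7.4.1), and neither schedule has a tolerability row, so part of the overlap comes from the protocol.

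Most of this stands, and it limits the severity. It does not restore the summary. Section 10.4.5.2 is the only protocol analysis text specific to this endpoint, and a listing is not an endpoint analysis.

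A reader might also infer more than the texts support:

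- *That the SAP redefines tolerability exclusively as related AEs.* The verb in 7.6.3 is *include*, so other findings could count. But the SAP then names no other content and no source for it.
- *That each subject yields a single count.* The SAP is silent on splitting.
- *That tolerability duplicates the related-AE component.* It is a subset. The component also covers immunosuppression and, in the SAP's category, unlikely related events.
- *That the percentage would be at its ceiling because every subject has surgery.* The documents give no rate of procedure-related AEs.

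**Conclusion.** The point holds in this form: SAP 7.6.3 leaves out the by-symptom, by-time-point summary that the protocol still plans. It describes a separate component of the Cohort 1 primary endpoint through AEs judged related to product or procedure, with no stated limit to the named symptoms or the implant site. When treatment-emergent, those AEs are already within tables vii and viii of SAP 7.2.7. The departure is not logged as an analysis change.

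The size is one descriptive table, about 80 counts per treatment group on the illustrative list of symptoms. No hypothesis test is affected, and the dates and outcomes of reported AEs remain in the listing. The change should be made, but the conduct of the trial does not depend on it.

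A reader might conclude that symptoms must be counted whatever their cause. Neither document says so. The protocol text is silent on attribution, which leaves a choice that the SAP should state.

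The conclusion assumes that no separate symptom form exists beyond what the two documents describe. Such a form would change the data source, but the SAP would still plan no table from it.

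**What to change.** In SAP 7.6.3:

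1. Restrict the endpoint to a fixed list of implant-site and tolerability symptom terms, built on those the protocol names.
2. Tabulate the number of subjects with each symptom at each post-implant visit, by treatment group and overall, in line with Protocol 10.4.5.2.
3. Name the data source. If it is AE terms with onset and end dates, let Day 1 stand in for the four-hour window unless clock times are collected: SAP 7.2.7 describes dates and study days only, from which four hours cannot be built. Protocol 7.4.1 does not name fever, tenderness or induration among the findings to monitor, so check that the chosen source captures them.
4. Keep the related-AE summary as a separate table, and state whether attribution is used in the symptom table.
5. Record the change in the revision log. If the sponsor prefers the related-AE summary alone, amend Protocol 10.4.5.2 to match.

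The cost is a term list and one extra table, with Day 1 only approximating the four-hour period. A dedicated symptom form would cost more and is needed only if AE records are judged inadequate.

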#### 8. INTERIM ANALYSIS

No decision-making interim analyses (e.g., for early stopping for efficacy or futility, or for modification to the planned enrollment) are planned. A DSMB will review all accumulated data when at least a minimum of three (3) Cohort 1 subjects complete the Week 4 visit, in order to make a recommendation on enrollment of Cohort 2. In addition, a descriptive analysis may be produced when all subjects reach their Week 26 visit to support regulatory discussions. This report, if produced, will summarize key safety and efficacy endpoints for these subjects.

## 9. DATA SAFETY MONITORING BOARD (DSMB)

An independent DSMB will meet at specified times throughout the study to review the accumulation of data. The DSMB will consist of at least 3 members, including a statistician. No Investigator involved in the trial or anyone connected to the Sponsor or participating vendors such as a CRO may be a member of the DSMB. Based on the review of the study data, the DSMB may make recommendations regarding the conduct of the study. These may include, but are not limited to, amending safety monitoring procedures, modifying the protocol or consent, terminating the study, or continuing the study as designed. The discussions and decisions of the DSMB will be summarized in written minutes and provided to the Sponsor. When necessary, summary DSMB minutes may be distributed to participating sites for submission to Institutional Review Boards or Ethics Committees. A separate DSMB Charter will direct the activities of the Board.

The approximate timing of DSMB meetings are noted below:

- After a minimum of three (3) subjects from Cohort 1 have reached the Week 4 clinic visit and the results are available, the Sponsor then has the ability to request the DSMB to meet. The available cumulative data collected in all subjects from Cohort 1 up until that time will be evaluated by the DSMB. Based on review of the available data, the DSMB will make a recommendation on the enrollment of Cohort 2. The DSMB will not meet regularly during Cohort 1 unless there is a related AE that requires an independent DSMB review.
- Quarterly during the first year of Cohort 2, and thereafter every three (3) to six (6) months until the last visit of the last Cohort 2 subject has occurred.

Additional safety event adjudication committees may be established as appropriate. As described above, individual committee charters will provide specific descriptions of the scope of responsibilities and the processes and definitions used to review and assess specific safety events and to trigger the start of Cohort 2 enrollment.

# 9.1 Internal Efficacy and Safety Review

After the last subject in Cohort 2 passes Visit 11 (Week 26), cumulative data from all Cohort 1 and Cohort 2 subjects will be assembled and sent to the DSMB and Sponsor for review. If the Sponsor believes the efficacy data appear robust, and the DSMB believes the safety data are appropriate, the Sponsor may choose to proceed to an End-of-Phase 2 (EoP2) meeting with the FDA to discuss next steps.

# 10. SAMPLE SIZE AND POWER CALCULATIONS

At least three (3) and up to approximately fifteen (15) subjects will be enrolled in Cohort 1. Approximately 60 subjects will be enrolled in Cohort 2, for a total enrollment of up to 75 subjects in both cohorts.

A sample size of 60 subjects in Cohort 2 will enable staggered enrollment of cadres of subjects allowing for testing of alternate device configuration and/or surgical implant technique (e.g., pharmacological intervention, implant site, etc.) in order to improve engraftment and cell survival outcomes. This approach will drive VC-02 engraftment optimization.

Once the optimized device configuration and surgical implant technique is determined, a sample size of 40 subjects implanted under those conditions will provide

ince Cohort 1 has the primary objective of evaluating initial safety and tolerability, these subjects will not contribute MMTT data for the Week 26 analysis.

If the minimal level of detection for C-peptide is 0.20 ng/mL, this would give an AUC of 0.8 ng x hour/mL for the 4-hour MMTT. A sample size of 40 subjects will provide

For the 2-hour MMTT, a sample size of 40 subjects will provide

# 12. APPENDICES

# 12.1 Appendix A: Schedule of Assessments

# 12.1.1 VC02-101 Cohort 1 and Cohort 2

	V1 a Screen	V2 Screen	V3 Enroll	V4	V5	V6	V 7	V8	V9	V10	V11	V12	V13	V14	V15	V16	V17 or ET	V18 Follow- Up
Assessments	Wk -5	Wk -4	Day 1	Day 2	Wk 2	Wk 4	Wk 8	Wk 12	Wk 16	Wk 20	Wk 26	Wk 39	Wk 52	Wk 65	Wk 78	Wk 91	Wk 104	Wk 105
Visit Windows		+14d		+1d	+/- 2d	+/-3d	+/- 7d	+/- 7d	+/- 7d	+/- 7d	+/- 7d	+/- 14d	+/- 14d	+/- 14d	+/- 14d	+/- 14d	+/- 7d	+/- 3d
Informed Consent	x																	
Entry Criteria	x	х	X															
Med History / Prior Meds	x																	
12-lead ECG	x										Х		Х				Х	
Physical Exam (Complete)	x										х		х				х	
Physical Exam (Abbreviated)			X		х	х		х				х			x			
Physical Exam (Targeted)				x														X
Height	x																	
Weight / Vitals	x	x	X	X	Х	х	X	Х	x	x	х	х	Х	Х	X	X	Х	x
Clarke Survey	x								x		х	х	Х		X		х	
Immunosuppression Drug Dosing							·	X (adj	just dos	sing as 1	needed)							
Dispense / Review CGM Data		х	Х	х	х	х	х	х	X	x	х	х	х	х	x	x	х	
Dispense / Review Diary Data		х	X	х	х	Х	x	х	x	х	х	х	х	х	x	x	х	
Dispense / Review SMBG Supplies		х	х	х	х	х	х	х	х	х	Х	х	Х	х	х	х	Х	
Implantation Procedure			X															
Explantation Procedure		X (time-points as determined by Sponsor)								х								

CONFIDENTIAL

Page 48 of 52

	V1 a Screen	V2 Screen	V3 Enroll	V4	V5	V6	V 7	V8	V9	V10	V11	V12	V13	V14	V15	V16	V17 or ET	V18 Follow- Up
Assessments	Wk -5	Wk -4	Day 1	Day 2	Wk 2	Wk 4	Wk 8	Wk 12	Wk 16	Wk 20	Wk 26	Wk 39	Wk 52	Wk 65	Wk 78	Wk 91	Wk 104	Wk 105
Ultrasound - Safety Evaluation							х		х		х		х		x		х	
Ultrasound - Pre-Explant a						X (ti	me-poi	ints TB	D bas	sed on	expla	nt pro	cedure	s)			х	
Video and Photos b			X		Х	(additio	nal tin	ne-poin	ts TB	D bas	ed on	explan	t proc	edures	;)		X	
AE and Concomitant Medications		х	Х	х	х	Х	х	х	х	X	x	x	х	x	x	x	х	x
ICD for Follow-Up Study c																		х
Central Laboratory Tests or Study-Provided Testing Kits																		
Drug Screen d	x		X															
HBsAg, HCV, HIV	X																	
CMV IgG and IgM g	1	х											Х				х	
CMV PCR	Ì	х						Х			х							
EBV IgG	x																	
Hematology & Chemistry	x	х	X		Х	х	X	х	x	x	x	х	Х	X	x	X	х	
HbA1c	x		X						x		х		Х		x		х	
Follicular Stimulating Hormone	x																	
Urine Pregnancy Teste	x		X										Х				x	
Thyroid Stimulating Hormone f	х																	
Quantiferon TB	X																	
SOGCT C-peptide	X																	
Ultrasensitive C-peptideh		x					Х	х	x	X	х	х	Х					

	V1 a Screen	V2 Screen	V3 Enroll	V4	V5	V6	V7	V8	V9	V10	V11	V12	V13	V14	V15	V16	V17 or ET	V18 Follow- Up
Assessments	Wk -5	Wk -4	Day 1	Day 2	Wk 2	Wk 4	Wk 8	Wk 12	Wk 16	Wk 20	Wk 26	Wk 39	Wk 52	Wk 65	Wk 78	Wk 91	Wk 104	Wk 105
2-hr MMTT/C-peptide & Glucose							х	х	x	х		Х		х		Х		
4-hr MMTT/C-peptide & Glucose		х			3	б					х		х		x		х	
Urinalysis	X												1					
Urine Albumin/Creatinine		Х									х		х		x		х	
Fasting Lipid Panel	X										х		х				х	
Immune Panel		Х				х			x		х		х				х	
Reserve Blood Samples	Х			S2	с	8		×			х		х		x		х	
Local Laboratory Tests																		0
Immunosuppression Drug Levels & Safety Panels				X (frequency as described in Section 7.11.3)														
a. Pre-explant unit loca depending on anatom					t the di	scretion	of the	Invest	igator	. Uni	t locat	ion m	ay be	determ	ined v	ia pal	pation	8
b. Video and/or photog but are otherwise not	raphs of t t required	he surgi l.	cal proc	edure	or impl	antation	anato	mical 1	ocatic	ons are	e to be	captu	red on	ly if r	equest	ed by	the Sp	onsor
c. A separate consent d	ocument	will be p	rovided	to the	e subjec	t for the	follow	w-up st	udy.									
d. The Visit 1 drug scre provided kit.	een sampl	e will be	e analyz	ed at t	he cent	ral lab.	The V	isit 3 c	lrug s	creen	is to b	e conc	lucted	locall	y usin	g the s	study-	
e. The urine pregnancy commences. Visit 17											s must	be av	ailablo	e befoi	e the	implan	t proc	edure
f. FSH testing only req	uired for	post-me	nopausa	l wom	en who	are not	using	contrac	eption	n.								
g. CMV IgM is not test were negative.	ed at Visi	it 2 (only	y IgG).	CMV	IgG an	d IgM te	sting i	s perfo	rmed	at Vis	it 13 a	nd Vi	sit 17	only i	f previ	ous te	st resi	ults
h. Ultrasensitive C-pep	tide samp	les to be	collected	l in con	iunction	with MMT	Ts nre-s	timulatio	n (time	= 0	nd nort	ctimulat	ion at th	a 00 m	inuta ( )	/ 10 mi	autoc) ti	manaint

#### 12.1.2 VC02-102 Cohort 1

	Vl Screen	V2 Screen	V3 Enroll	V4	V5	V6	V 7	V8	V9 or ET	V10 FU
Assessments	Wk -4	Wk -3	Day 1	Day 2	Wk 2	Wk 4	Wk 8	Wk 12	Wk 16	Wk 17
Visit Windows				+ld	+/-2d	+/-3d	+/-7d	+/-7 d	+/-7d	+/-7 d
Informed Consent	Х									
Entry Criteria	Х	Х	Х							
Med History / Prior Meds	х									
12-lead ECG	х								х	
Physical Exam (Complete)	х								х	
Physical Exam (Abbreviated)			Х		Х	х		Х		
Physical Exam (Targeted)				х						х
Height	х									
Weight / Vitals	х	х	x	Х	х	х	Х	х	х	х
Immunosuppression Drug Dosing		X (adjust dosing as needed – Protocol Section Error! Reference source not found.)								
Dispense / Review CGM Data		х	x	Х	х	х	Х	х	х	
Dispense / Review Diary Data		х	x	Х	х	х	Х	х	х	
Dispense / Review SMBG Supplies		х	x	Х	х	х	Х	х	х	
Implantation Procedure			x							
Explantation Procedure				X (ti	me-points a	as determi	ned by Sp	onsor)	х	
Ultrasound - Safety Evaluation							Х		х	
Ultrasound - Pre-Explant a				X (tin	ne-points de	etermined	by explan	tations)	х	
Video and Photos b			x	X (tin	ne-points de	etermined	by explan	tations)	х	
AE and Concomitant Medications		Х	Х	Х	Х	х	Х	Х	х	х
ICD for 3-Year Follow-Up Study c									2	C
Central Laboratory Tests or Study-P	rovided Te	sting Kits								
Drug Screen d	Х		X							
HBsAg, HCV, HIV	Х									
Hematology & Chemistry	Х	Х	х		Х	х	Х	Х	х	

CONFIDENTIAL

	Vl Screen	V2 Screen	V3 Enroll	V4	V5	V6	V 7	V8	V9 or ET	V10 FU
Assessments	Wk -4	Wk -3	Day 1	Day 2	Wk 2	Wk 4	Wk 8	Wk 12	Wk 16	Wk 17
HbA1c	х		х						х	
Urine Pregnancy Test e	Х									
Follicular Stimulating Hormone f	х									
Thyroid Stimulating Hormone	Х									
Quantiferon TB	х									
Urinalysis	х									
Urine Albumin/Creatinine		х							х	
Fasting Lipid Panel	Х								х	
Immune Panel		х				х			х	
Reserve Blood Samples			2	K(time-	p oin t s as	d et e rmi	n ed b y S	p on s or )		
Local Laboratory Tests										
Immunosuppression Drug Levels				X ( frequency as described in Protocol Section Error! Reference source not found.)						erence
Immunosuppression Safety Panels				X ( frequency as described in Protocol Section Error! Reference source not found.)						

a. Pre-explant unit location ultrasound only required at the discretion of the Investigator. Unit location may be determined via palpation dependingon anatomical location (Section Error! Reference source not found.).

- b. Video and/or photographs of the surgical procedure or implantation anatomical locations are to be captured only if requested by the Sponsor but are otherwise not required.
- c. A separate consent document will be provided to the subject for the follow-up study.
- d. The Visit 1 drug screen sample will be analyzed at the central lab. The Visit 3 drug screen is to be conducted locally using the study-provided kit.
- e. The urine pregnancy test is administered locally using the study-provided kit.
- f. FSH testing only required for women.

